4. Tumor types of origin include gastric, pancreatic, hepatobiliary, colorectal, and sarcoma. Tumors may be primary or metastatic to solid or hollow intra-abdominal organs.
5. Subject must understand the investigational nature of this study and sign an Independent Ethics Committee/Institutional Review Board approved written informed consent.
6. Subject must have a skin prick test pre-operatively (at the time of the preoperative visit and after signed informed consent for entry into this clinical trial is given) to determine any sensitivity to fluorescein.

*Exclusion criteria:*

1. Uncontrolled intercurrent illness including, but not limited to, ongoing or active infection, symptomatic congestive heart failure, unstable angina pectoris, cardiac arrhythmia, or psychiatric illness/social situations.
2. Renal dysfunction as defined as a GFR < 45.
3. Liver dysfunction as defined by Child-Pugh score > 5, or LFT's 1.5x above normal range.
4. Any known allergy or prior reaction to fluorescein or a positive skin prick test to fluorescein.
5. Pregnant or nursing female subjects, determined preoperatively with a urine pregnancy test.
6. Unwilling or unable to follow protocol requirements.
7. Any condition which in the Investigators' opinion deems the patient unsuitable (e.g., abnormal EKG, including T wave inversion, elevated T waves, prolonged QRS interval, or conduction blocks) or that requires further work-up (including cardiac echo or stress test).
8. Any condition that excludes surgery as the standard of care (e.g. high disease burden where alternative treatments like systemic chemotherapy would be preferred).

Primary and Secondary Endpoints/Criteria for Evaluation:

*Primary endpoint:* A patient will be deemed a success if each of the following parameters were measured:

1. Identify tumor associated vessels and measure vessel diameters
2. Determine vessel density per 10x field
3. Visualize vital dyes within the tumor-associated vessels (fluorescein)
4. Calculate the blood flow velocity of the tumor-associated vessels and tissue penetration of fluorescein as a marker of vessel permeability.

Measurements will be obtained before and after any tumor vessel manipulation with either bolus fluids or vasopressors.

*Secondary endpoints:*

1. Post-operative comparison of the microvasculature of tumor with normal tissue (e.g. peritoneum) in each individual subject using vessel diameters, vessel density, detection of intravital dye and flow rates.

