## **5 SUBJECT SELECTION**

Patients who are scheduled to undergo surgical resection in the operating room who can provide informed consent, have a good performance status (ECOG  $\leq 2$ ), and have no known allergy or prior reaction to fluorescein, are eligible.

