## **6 STUDY PROCEDURES**

### **6.1 BASELINE EVALUATIONS**

Standard presurgical assessment with labs and studies as determined by the preoperative Anesthesia clinic based upon their established guidelines.

The following will be performed within 1-4 weeks prior to the planned microscopic observation:

- Informed consent: Must be completed prior to receiving any study-related procedures.
- Medical history
- Physical examination, including vital signs (i.e., temperature, heart rate, respiratory rate, blood pressure, body weight, and height).
- If determined to be eligible for the study and after giving informed consent, a skin-prick test to determine sensitivity and risk of anaphylaxis to fluorescein will be performed by the Principal Investigator. For testing allergic response to fluorescein, a sterile Duotip® lancet (Lincoln Medical, USA) is used in 2 separate areas of skin on the forearm. The skin-pricks will include approximately 4 microliters of 10% or 25% fluorescein administered in areas of skin prepped with an alcohol pad. After 30 minutes, the appearance of a wheal greater than 3 mm in diameter is considered a positive test result. If a positive test is noted, the patient will no longer be eligible for this study. For comfort and relief of any skin irritation/pruritis, the patient will be offered an anti-histamine (fexofenadine [Allegra®] 30 mg po x 1) following the skin-prick test if necessary.
- If indicated by anesthesia pre-op assessment (standard operating procedure for pre-op clinic)
  - Hematology [i.e., CBC (with or without differential, auto or manual), ANC, and platelets].

- A complete metabolic panel (CMP): chloride, Co2, potassium, sodium, BUN, glucose, calcium, creatinine, total protein, albumin, total bilirubin, alkaline phosphatase, AST, ALT, A/G ratio, BUN/creatinine ratio, osmol (Calc), anion gap).
- If indicated by anesthesia pre-op assessment (standard operating procedure for the pre-op clinic) – 12-lead electrocardiogram, chest x-ray, and/or pulmonary function tests if indicated. These tests are not strictly required to support eligibility for this study, but if indicated and performed, may exclude the patient from receiving a general anesthetic and therefore, a wide excision performed in the operating room (thereby excluding the patient from this study).

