### Study Calendar

	Pre-operative Visit	Surgery	Post-operative Visit
History and Physical	X		
Informed consent	X		
Fluorescein skin prick test	X		
Tests as medically indicated	X		

Surgical resection with IVM		X	
Post-surgical monitoring in recovery and inpatient stay		X	
Review of pathology			X
Routine cancer surveillance			X

- At the completion of the surgery, if gross tumor is entirely debulked (R0 resection), then patients are considered disease free. Treatment response will be based upon the presence of a recurrence of tumor at either the primary site, locoregional recurrence (peritoneum), or metastatic sites.
- The time to recurrence will determine the standard length of clinical follow up. However, for this study, a 10-year limit will be placed on clinical data collection during the standard clinical follow up. After a patient is enrolled, the duration of data collection will end at 10 years from the time of microscopic observation (surgery). These data (time of recurrence and/or survival) will be correlated with findings from the one-time, initial IVM observation for the defined 10-year period of data collection.
- The surveillance data (no evidence of disease, disease recurrence, death) will be stored in a secured database and matched to the microscopic observation data. These data will serve as the basis for statistical comparisons of microscopic findings and clinical outcomes to be performed by our study statistician as described in section 9.

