A matched analysis will be performed for observations of microvasculature between the tumor and normal tissue. For dichotomous variable comparisons between vessel structure (normal vs aberrant), vessel branching patterns (normal vs aberrant), or detection of intravital dye (present vs absent), a McNemar's test will be performed. For continuous variable comparisons between blood vessel density and average blood flow rate, a paired t test will be performed.

Associations between characteristics for the baseline (normal peritoneal microvasculature observed surrounding the tumor) and tumor itself will be depicted with graphics, correlations, and model results.

Similar analyses will be performed to compare baseline observations with those performed after fluid bolus and/or vasopressor administration.

Adverse event and complication rates will be described using upper one-sided 95% Clopper Pearson confidence limits.

Overall survival will be defined as the duration of time from diagnosis to time of death. Disease specific survival will be defined as the time from surgery to death due to recurrence. Overall survival and disease specific survival will be generated using standard Kaplan-Meier methodology.

A maximum of 50 subjects will be enrolled in this study (initially 10 to determine feasibility and then 40 additional subjects if deemed feasible). The accrual rate is estimated at 1-2 subjects per month, and the estimated study duration is 30 months (2.5 years).

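### Overall survival is counted from diagnosis with no delayed entry, but only patients alive at surgery can be imaged, so the curve includes guaranteed survival time

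*Combined protocol and SAP*

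**What the plan says.** Section 9 (Statistical Methodology) gives two survival definitions with different starting points. For OS: "Overall survival will be defined as the duration of time from diagnosis to time of death". For the disease-specific endpoint: "Disease specific survival will be defined as the time from surgery to death due to recurrence". The only method named is: "Overall survival and disease specific survival will be generated using standard Kaplan-Meier methodology". Delayed entry, a landmark at surgery and adjustment for the diagnosis-to-surgery interval appear nowhere in the documents.

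Everything else on this objective is anchored at surgery:

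- Section 4.2 places the HIVM observation in the operating room, once the tumor is exposed.
- The notes under the Study Calendar (Section 6.3) stop data collection 10 years after the microscopic observation. They say that recurrence and survival data "will be correlated with findings from the one-time, initial IVM observation for the defined 10-year period" of collection.
- Section 5 describes those eligible as "Patients who are scheduled to undergo surgical resection in the operating room who can provide informed consent", so entry is conditional on having reached the point of planned surgery.

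The documents do not say which diagnosis is meant. Synopsis inclusion criterion 4 allows that "Tumors may be primary or metastatic to solid or hollow intra-abdominal organs". For a resected metastasis, the date could be that of the primary cancer or that of the lesion being removed.

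**The concern.** Secondary objective 3 (Section 3.2) correlates HIVM findings with OS. A patient contributes to that analysis only by being alive at the operation. Section 6.1 says of the baseline work-up: "The following will be performed within 1-4 weeks prior to the planned microscopic observation". An enrolled patient could therefore die between consent and surgery, but would have no HIVM data to correlate. Among imaged patients, the interval from diagnosis to surgery cannot contain a death.

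OS from diagnosis is a legitimate quantity, but when patients come under observation only at surgery it needs left truncation (delayed entry). Standard Kaplan-Meier instead treats every imaged patient as at risk from diagnosis.

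Three things follow. The OS curve sits too high. OS and disease-specific survival cannot be read on the same time axis. Two analysts could derive different OS times for the same patient with metastatic disease.

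**Working it through.** **Inputs.** From the documents: OS origin at diagnosis, disease-specific survival origin at surgery, standard Kaplan-Meier (Section 9); HIVM at surgery (Section 4.2); 10-year limit from surgery (Study Calendar notes); at most 50 patients (Section 9). Not in the documents, hence assumed: survival after surgery, the diagnosis-to-surgery gap g, any HIVM grouping and any survival test. The plan has no survival figure to reproduce.

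**Step 1: shift of the curve.** Let survival after surgery be exponential with median m months, S(t) = 0.5^(t/m). With a fixed gap g, standard Kaplan-Meier from diagnosis estimates 1 for t ≤ g and 0.5^((t−g)/m) for t > g. The median rises by exactly g.

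For m = 24:

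- 12 months: 0.5^(12/24) = 0.707 from surgery. From diagnosis: 0.5^(9/24) = 0.771 (g = 3) and 0.5^(6/24) = 0.841 (g = 6).
- 24 months: 0.5^(24/24) = 0.500 from surgery. From diagnosis: 0.5^(21/24) = 0.545 (g = 3) and 0.5^(18/24) = 0.595 (0.5946 before rounding; g = 6).

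Range over other assumed medians:

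| Median after surgery (months) | Gap (months) | 12-month OS | 24-month OS | Median as read (months) |
|---|---|---|---|---|
| 12 | 0 | 50.0% | 25.0% | 12 |
| 12 | 3 | 59.5% | 29.7% | 15 |
| 12 | 6 | 70.7% | 35.4% | 18 |
| 24 | 0 | 70.7% | 50.0% | 24 |
| 24 | 3 | 77.1% | 54.5% | 27 |
| 24 | 6 | 84.1% | 59.5% | 30 |
| 36 | 0 | 79.4% | 63.0% | 36 |
| 36 | 3 | 84.1% | 66.7% | 39 |
| 36 | 6 | 89.1% | 70.7% | 42 |

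This shift needs no imbalance between HIVM groups.

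**Step 2: HIVM-OS association, gap unrelated to HIVM.** With no true effect, gap plus survival has the same distribution in both groups, so a test from diagnosis remains valid. In simulation (25 v 25, median 24 months, censoring 120 months after surgery, nominal 5%) it rejected in 5.6–5.9% of trials from diagnosis and 6.0% from surgery. A true hazard ratio of 2 was estimated from diagnosis as 2.00, 1.97 and 1.87 for exponential gaps of mean 3, 6 and 12 months.

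**Step 3: gap that differs by HIVM finding (direction only).** Suppose, as an extreme, that mean gaps are 2 months in one group and 12 in the other:

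| True hazard ratio | Group with the longer gap | From diagnosis | From surgery | From diagnosis, delayed entry |
|---|---|---|---|---|
| 1 | comparison group | 0.74 | 0.98 | 0.98 |
| 2 | higher-hazard group | 1.28 | 1.96 | 1.95 |
| 2 | lower-hazard group | 3.09 | 2.14 | 2.17 |

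Distortion can go either way, and both remedies remove it.

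**Step 4: what moving the origin does not do.** Suppose no HIVM effect, median survival 36 months in primary and 18 in metastatic disease, mean gaps 2 months (primary) and 6 or 12 (metastatic), and metastatic shares of 30% v 70% or 20% v 80% in two groups of 25. A crude log-rank test at 5% then rejects in about 15–28% of trials from surgery and 9–21% from diagnosis. From diagnosis the two biases partly cancel: the longer gap flatters the group that does worse. With milder medians of 27 v 21 months the figures are 6.6–8.9% and 5.2–6.2%. Stratifying by primary/metastatic status, from surgery, brings the 36 v 18 case to 5.2–5.6%.

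**The case against.** The strongest reply has four parts.

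**The guaranteed time is not universal.** Section 5.1 asks for a visible tumor that meets indications for resection, not prior histology, and final pathology follows surgery by 5–7 days (Section 3.3). A patient first diagnosed at surgery has no gap. This stands, and the conclusion is limited to patients diagnosed before surgery.

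**No test is planned.** Section 9 names only Kaplan-Meier, with no log-rank test, Cox model, alpha level or HIVM grouping for survival. A reader might infer that the diagnosis origin will produce false HIVM-OS associations. The documents do not support that: they show no difference in gap by HIVM finding, and any error rate depends on invented groupings. For example, with 40 v 10 patients and equal survival after surgery, simulated type I error from diagnosis is 7.3–12.6% (about 6% from surgery) if the larger group is more often metastatic. If the smaller group is, it is 5.4–6.2% (5.7–6.7% from surgery). Such figures are illustrations, not properties of the plan.

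**Re-anchoring can raise false positives in a crude comparison.** Step 4 shows this. It is no argument for keeping a biased clock because it offsets confounding by chance, but it does mean that labelling the comparison unadjusted is not enough.

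**The consequence is limited.** Survival is an unpowered secondary objective, and OS from surgery could be computed at analysis anyway. Both are true, but the definition as written would still give the shifted curve.

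**Conclusion.** The point holds for the OS definition and the curve it produces. Followed as written, Section 9 credits imaged patients with survival time in which they could not have died, on a different clock from HIVM, disease-specific survival and the 10-year window. Under the 24-month assumption the overstatement is about 6 to 13 percentage points at 12 months (71% to 77% or 84%) and 5 to 9 points at 24 months (50% to 55% or 59%). It is zero for a patient first diagnosed at surgery. These sizes rest on exponential survival and fixed gaps of 3 or 6 months, none of which the documents give.

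For the HIVM-OS association the supported claim is weaker. If the gap is unrelated to HIVM, type I error is kept and a hazard ratio of 2 is estimated as about 1.9–2.0. Larger distortion is possible in principle but not shown. Only secondary objective 3 is affected.

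**What to change.** In Section 9, define OS as the time from surgery (the HIVM observation) to death from any cause, with survivors censored at last contact and at most 10 years after surgery. If OS from diagnosis is also wanted, state which diagnosis counts for primary and for metastatic tumors, and analyse it with delayed entry at surgery.

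State that any HIVM-OS comparison is exploratory, and show a version stratified by primary/metastatic status beside the crude one.

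**Cost.** The surgery date is known for every imaged patient, so the new origin needs no extra data. Reported OS will look shorter and will not compare directly with series counted from diagnosis. Stratifying costs power: for a hazard ratio of 2 with 25 v 25 and a 24-month median in both disease types, about 65% falls to 54% (metastatic shares 30% v 70%) or 42% (20% v 80%).

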### 3.2 SECONDARY OBJECTIVES - PART II (40 PATIENTS):

1. Compare the microscopic observation of the tumor-associated vessels with normal tissue (peritoneal surface) in each individual subject.
2. Correlate the microscopic observations of the tumor-associated vessels with pathologic grade of tumor.
3. To correlate the microscopic observation of the microvasculature with tumor-specific and overall survival.

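### Disease-specific survival counts only death due to recurrence, so a cancer death from residual disease is not an event and the curve is overstated if any patient is incompletely resected

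*Combined protocol and SAP*

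**What the plan says.** The survival objective in Section 3.2 is: "To correlate the microscopic observation of the microvasculature with tumor-specific and overall survival". The Synopsis lists the same objective.

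Section 9 defines the two outcomes differently:

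- Overall survival: "Overall survival will be defined as the duration of time from diagnosis to time of death".
- Disease-specific survival: "Disease specific survival will be defined as the time from surgery to death due to recurrence".
- Method: "Overall survival and disease specific survival will be generated using standard Kaplan-Meier methodology". No censoring rule is given for either outcome.

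The notes to the Study Calendar (Section 6.3) set the disease status on which recurrence depends: "if gross tumor is entirely debulked (R0 resection), then patients are considered disease free". They continue: "Treatment response will be based upon the presence of a recurrence of tumor at either the primary site, locoregional recurrence (peritoneum), or metastatic sites". The data to be stored are listed as "The surveillance data (no evidence of disease, disease recurrence, death", and the list ends there.

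On who may be enrolled, the Synopsis says: "Tumors may be primary or metastatic to solid or hollow intra-abdominal organs". Section 5.1 asks for a deep space tumor with an indication for resection. It does not make complete resection a condition of entry or of staying in the analysis.

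**The concern.** Recurrence presupposes a disease-free interval. The calendar notes grant disease-free status conditionally, so the protocol itself allows that some patients will not have it. It does not say how their cancer deaths are classified. Under the Section 9 wording such a death is not a DSS event, and in a standard Kaplan-Meier analysis the patient would be censored at death.

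At stake is the disease-specific half of the survival objective. The Synopsis (Aim 1) hopes that the microscopy findings will serve as a predictive biomarker, and outcome data are collected for 10 years from surgery. A reported DSS that omits some cancer deaths is not the tumor-specific survival the objective names. The surveillance categories fixed at the start also determine whether the omission can be corrected later.

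**Working it through.** **Step 1: read the sections together.** The plan gives no event count, survival rate or power for DSS, so there is no figure to reproduce.

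- Section 3.2 names tumor-specific survival. Section 9 limits the event to death after recurrence, which is narrower.
- Study Calendar notes: disease free only if gross tumor is entirely removed. The status of other patients is undefined.
- Synopsis and Section 5.1: metastatic tumors are allowed and an indication for resection is needed, but complete resection is not.
- Section 4.2: patients are replaced for equipment faults or unrelated events that end the surgery. Incomplete resection is not on that list, so these patients stay in.
- Study Calendar notes: no surveillance category for persistent or progressive disease, and cause of death is not listed.

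No other section repairs the definition.

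**Step 2: illustrate the size.** Every input here is an assumption:

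- a share q of patients is not disease free after surgery, from 5% to 30%;
- times to cancer death are exponential, with median 5 years if disease free and median m of 1.5 to 5 years if not;
- there are no deaths from other causes, and follow-up is complete to 10 years;
- cancer deaths in patients never disease free are censored at death.

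Five-year DSS counting all cancer deaths:

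S_all = (1 − q) × 2^(−5/5) + q × 2^(−5/m)

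Five-year Kaplan-Meier DSS counting recurrence deaths only, with d = 1/m − 1/5:

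S_rec = [(1 − q) × 2^(5d) + q]^(−0.2/d), and when m = 5, S_rec = 2^(−(1 − q))

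Worked case, q = 0.20 and m = 1.5:

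- S_all = 0.80 × 0.5 + 0.20 × 0.0992 = 0.420
- 5d = 5/1.5 − 1 = 2.333, 2^2.333 = 5.040, 0.2/d = 0.4286
- S_rec = (0.80 × 5.040 + 0.20)^(−0.4286) = 4.232^(−0.4286) = 0.539
- Overstatement = 53.9% − 42.0% = 11.9 points

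Same share, m = 5 (equal prognosis): S_all = 0.500, S_rec = 2^(−0.8) = 0.574, overstatement 7.4 points.

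| Share q | m = 1.5: all / recurrence only | m = 5: all / recurrence only | Overstatement (points) |
|---|---|---|---|
| 5% | 48.0% / 50.9% | 50.0% / 51.8% | about 2 to 3 |
| 10% | 46.0% / 51.8% | 50.0% / 53.6% | about 4 to 6 |
| 20% | 42.0% / 53.9% | 50.0% / 57.4% | about 7 to 12 |
| 30% | 38.0% / 56.3% | 50.0% / 61.6% | about 12 to 18 |

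A simulation of 400,000 patients per setting agreed with these values to within 0.1 point.

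**Step 3: event counts.** Over 10 years, for q = 0.20 and m = 1.5, expected cancer deaths among 50 patients are 50 × [1 − (0.80 × 0.25 + 0.20 × 0.0098)] = 39.9. Those counted are 50 × 0.80 × 0.75 = 30.0. If only the 40 Part II patients are used, as Section 3.2 suggests, both scale by 0.8, to 31.9 and 24.0. The percentages in Step 2 do not depend on the number enrolled.

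**Step 4: the association with microscopy findings.** Cox models were fitted to 20,000 simulated patients per setting, with half having abnormal findings, a true within-stratum hazard ratio of 2, and medians of 5 and 1.5 years.

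| Share incompletely resected, abnormal vs normal findings | HR, all cancer deaths | HR, recurrence deaths only |
|---|---|---|
| 30% vs 10% | 2.27 | 1.93 |
| 20% vs 5% | 2.17 | 1.91 |
| 20% vs 20% | 1.87 | 2.08 |
| 10% vs 10% | 1.92 | 2.03 |

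The hazard ratio moves down in two settings and up in two.

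**The case against.** The strongest reply is that recurrence is loose wording for death from the cancer, since the objective says tumor-specific, and that few patients will be affected. The Synopsis excludes patients for whom surgery is not standard of care, giving high disease burden as an example, and requires a tumor that needs resection. If everyone is completely resected, the two definitions coincide. DSS is also a secondary, descriptive outcome with no test or decision attached.

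Much of this stands. It limits the likely size, and it makes this a repair to a secondary endpoint. It does not remove the defect. The entry criteria do not guarantee complete resection. If the wording is loose, someone in an open-label study must decide case by case which cancer deaths count, possibly knowing the microscopy findings.

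Several stronger readings are tempting but unsupported:

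- A reader might infer that the whole survival objective is biased. Overall survival runs to death from any cause, so these deaths all count there.
- A reader might infer that the association with microscopy findings is pulled toward the null or reversed. The direction depends on how residual disease is distributed between patients with normal and abnormal findings, which the documents do not tell us. No setting examined showed reversal.
- A reader might infer that the plan correlates a recurrence time for every patient. The calendar note refers to recurrence and/or survival, so patients without a recurrence time can contribute through survival.
- A reader might infer that the missed deaths come from the patients with the worst prognosis. The documents do not say so, and the overstatement does not need it: it is 7.4 points at a 20% share even with equal prognosis.

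**Conclusion.** The DSS definition is wrong as written for the objective it serves. This follows from the text alone: any cancer death in a patient never disease free is excluded, and DSS is then too high. How far too high cannot be settled from the documents, because neither the share of incompletely resected patients nor their death rates are given. The percentage-point figures are illustrations under exponential survival, the stated medians and censoring at the uncounted death. They should not be read as estimates for this trial. Confidence is high that the definition has this defect and low on how much it will matter. It should be corrected, but it does not touch the feasibility endpoint.

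**What to change.** In Section 9, define the DSS event as death due to the study cancer, whether recurrent, persistent or progressive, and state how deaths from other causes are handled.

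In the Study Calendar notes (Section 6.3), add a category for persistent or progressive disease and a field for cause of death. The revised event cannot be derived from the three categories now listed. Limit any time-to-recurrence analysis to patients who are disease free after surgery.

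The cost is a few sentences and two extra data fields taken from follow-up records. The number of patients and their care do not change. Reported DSS may be lower than under the present wording.

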### **5.1 INCLUSION CRITERIA**

1. Age  $\geq 18$  years of age.
2. Have an ECOG Performance Status of  $\leq 2$ . Refer to Appendix B.
3. Have measurable tumor by direct visualization (visible lesion typically  $> 0.5$  cm in maximal diameter).
4. Deep space tumor that meets indications for resection.
5. Subject must understand the investigational nature of this study and sign an Independent Ethics Committee/Institutional Review Board approved written informed consent form prior to receiving any study related procedure.
6. A negative skin-prick test to fluorescein.

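### Section 9 names no method that relates vessel findings to survival or tumor grade, and does not account for tumor type, so secondary objectives 2 and 3 cannot be answered as written

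*Combined protocol and SAP*

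**What the plan says.** **Objectives.** Section 3.2 lists "Correlate the microscopic observations of the tumor-associated vessels with pathologic grade of tumor" (objective 2) and "To correlate the microscopic observation of the microvasculature with tumor-specific and overall survival" (objective 3). Section 9 repeats both as purposes of the 40 patients added in Part II.

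**Where the analysis should be.** The notes under the Study Calendar say that the surveillance data will be the basis for "statistical comparisons of microscopic findings and clinical outcomes to be performed by our study statistician as described in section 9".

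**What section 9 contains.** For survival it gives two definitions and one sentence on method: "Overall survival and disease specific survival will be generated using standard Kaplan-Meier methodology". It names no grouping variable, log-rank test, regression model, covariate, stratum or effect measure. For grade it names nothing. McNemar's test and the paired t test are for tumor versus normal tissue and, by extension, for before versus after bolus or vasopressor. The one mention of models, that associations "will be depicted with graphics, correlations, and model results", concerns normal peritoneum and tumor.

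**Who is enrolled.** The synopsis states "Tumor types of origin include gastric, pancreatic, hepatobiliary, colorectal, and sarcoma" and "Tumors may be primary or metastatic to solid or hollow intra-abdominal organs". Section 5.1 does not list types at all: "Deep space tumor that meets indications for resection". Section 9 does not refer to tumor type.

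**The concern.** There are two linked problems.

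First, the reference to section 9 leads to no analysis. A statistician who follows section 9 to the letter will produce survival curves, but no estimate of how a vessel measure relates to survival, and nothing for grade. The choice of vessel measure, cutoff, model and adjustment would then be made after the data are seen.

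Second, tumor type is an obvious candidate for confounding. The eligible cancers can be expected to differ in prognosis and in how they are graded, and they may differ in vascularity. If so, a vessel measure can act as a label for tumor type and appear prognostic with no relation inside any one cancer.

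At stake is the second half of Aim 1, which hypothesizes that HIVM can serve as a predictive biomarker. The Part I feasibility decision is not affected.

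**Working it through.** **Step 1. Is there a figure to reproduce?** No. The only probabilities in section 9 concern the Part I rule of at least seven successes in ten. None is given for objectives 2 or 3.

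**Step 2. What does the named method deliver?** The Kaplan-Meier estimate is S(t) = product over death times of (1 - d/n), where d is deaths and n is the number at risk. No vessel measure enters it. It becomes a comparison only when a grouping is named, and an association only when a test or effect measure is added. Section 9 defines an abnormal HIVM observation by any of five criteria, but does not say that the curves will be split by it.

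**Step 3. How large could confounding by type be?** The only inputs from the documents are 50 patients (the maximum) and five types (synopsis). All else is assumed:

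- ten patients per type;
- exponential survival with medians of 1.5, 2, 3, 5 and 6 years;
- uniform censoring from 3 to 7.5 years (about 34 deaths);
- a normally distributed vessel measure with SD 1 within type and evenly spaced type means;
- no effect of the measure within any type.

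The gap is the distance from the lowest to the highest type mean. The test is the Cox score test: U = sum over deaths of (x - mean of x in the risk set), V = sum of the risk-set variances, reject if U²/V > 3.84. In the stratified version, risk sets are formed within type and U and V are summed over types. Ranges are over repeated runs of 600 to 4,000 simulated trials per setting. At 600 trials the simulation error at 5% is sqrt(0.05 × 0.95 / 600) = 0.9 percentage points.

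| Gap (SD) | Unstratified, order aligned with prognosis | Unstratified, order random |
|---|---|---|
| 0 | about 5% | about 5% |
| 0.5 | 7-8% | about 6% |
| 1.0 | 13-17% | 6-8% |
| 1.5 | 23-28% | 9-10% |

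Stratified by type, the rate is 4-7% over all settings.

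**Step 4. A second form of the check.** Here the vessel finding is a yes/no HIVM abnormality and the test is the log-rank test. The medians are the same, censoring is uniform from 36 to 60 months (about 30 deaths), and there are 4,000 trials per setting.

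| Abnormality prevalence, worst to best prognosis | Unstratified | Stratified |
|---|---|---|
| 50% in all types | 5.3% | 5.8% |
| 60% to 40% | 7.2% | 5.7% |
| 70% to 30% | 11.3% | 5.2% |
| 90% to 10% | 33.2% | 5.0% |
| 90% to 10%, equal survival in all types | 5.0% | 5.1% |

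The inflation needs both differences: it disappears when either vascularity or survival is equal across types.

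**Step 5. What can 50 patients show?** By Schoenfeld's formula (two-sided 5%, 80% power), the detectable hazard ratio is exp[(1.960 + 0.842) / sqrt(D × p × (1 - p))], with D deaths and a share p abnormal. With D = 30 and p = 0.5 it is exp(2.802 / 2.739) = 2.78; with 20 deaths it is 3.50 and with 40 deaths 2.43. A hazard ratio of 2 needs 2.802² / (0.25 × 0.693²) = 65.3, so 66 deaths, more than the 50 patients.

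Grade was not simulated. The same reasoning applies if grade and vascularity both differ by type, but no size is attached to it.

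**The case against.** The strongest reply is proportion. These are secondary objectives of a single-center, non-randomized study whose first part is a feasibility pilot. The only decision rule concerns feasibility, no alpha is attached to the survival objective, and the wording is only that findings will be correlated. This stands as a reason to label the analyses exploratory. It does not excuse leaving them unnamed when another part of the protocol says that section 9 describes them.

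It can also be said that curves split by normal versus abnormal HIVM are plainly intended. That is plausible, but it is not written, and it would still give no effect estimate and nothing for grade.

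A reader might infer more than the documents support:

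- **That the plan prescribes a pooled analysis.** It does not. It is silent on tumor type, and the unstratified Cox model examined above is not in the plan.
- **That any vessel measure differing by type will be associated with survival.** It can be, but only if the order of types by vascularity lines up to some degree with their order by prognosis. With random order, the rate at the same gaps is about 6-10%.
- **That 13-28% is this trial's error rate.** It belongs to an assumed, aligned ordering. The documents give no survival, type mix or vessel distribution by type.
- **That Kaplan-Meier curves are the method for grade.** They are named for survival only.

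Stratification is also not the only answer; covariate adjustment would serve. The list of five types may not be exhaustive, since section 5.1 does not limit the type.

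**Conclusion.** The point holds in two parts of different strength. That section 9 contains no association analysis for objectives 2 and 3 follows from the text alone and rests on no assumption. That tumor type can produce a false HIVM association is conditional: it requires vascularity and prognosis (or grade) both to differ by type. Under the assumed medians, the false-positive rate of an unadjusted survival analysis ranges from about 5% (no vascular gap) through about 6-10% (random order) to about 13-28% (aligned order, gap of 1.0-1.5 SD). Stratifying by type holds it near 5% in every setting tried. Primary versus metastatic disease raises the same question and was not simulated. The plan should be changed, but feasibility, the primary objective, is untouched.

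**What to change.** In section 9:

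1. **Survival.** Name Cox regression of overall and disease specific survival on one pre-named vessel measure, stratified by or adjusted for tumor type. State in advance the rule for merging small types, and say how primary versus metastatic disease is handled. Report the hazard ratio with its confidence interval. Kaplan-Meier curves can stay as description.
2. **Grade.** Name a type-stratified rank test, such as the van Elteren test, with the same type grouping.
3. **Status.** Label both analyses exploratory, given the hazard ratios that 50 patients can detect.

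The cost is a few sentences in section 9 and a small loss of efficiency in small strata. No new data should be needed, since tumor origin should be known from eligibility and from the pathology review in the Study Calendar. Merging types brings back some of the mixing, which is why the rule should be fixed before the data are seen.
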